12.2.3 Descriptive Statistics

Values will be calculated for the plasma concentrations and the PK parameters listed in [Section 12.1](#) using appropriate summary statistics to be fully outlined in the SAP.

12.2.4 Statistical Analysis

An ANOVA will be performed on the ln-transformed AUC_{0-t}, AUC_{0-inf}, and C_{max} using SAS[®] Proc Mixed. The ANOVA model will include sequence, treatment, and period as fixed effects, and subject nested within sequence as a random effect. Each ANOVA will include calculation of least-squares means (LSM) of the ln-transformed parameter as well as the LSM difference between treatments.

Ratios of geometric LSM (GLSM) will be calculated using the exponentiation of the difference between treatment LSM from the analyses on the ln-transformed AUC_{0-t}, AUC_{0-inf}, and C_{max}. These ratios will be expressed as a percentage, test relative to the reference (Treatment A vs. Treatment B).

Consistent with the two one-sided test, ⁶ 90% CIs for the GLSM ratios will be derived by exponentiation of the CIs obtained for the LSM difference between treatments resulting from the analyses on the ln-transformed AUC_{0-t}, AUC_{0-inf}, and C_{max}. The CIs will be expressed as a percentage, test relative to the reference (Treatment A vs. Treatment B).

Bioequivalence criteria will be met if the 90% CIs for the ratios of GLSMs of C_{max} and AUC_{0-inf} of MMF of the Test (Treatment A) to the Reference (Treatment B) fall within the limit of 80.00 and 125.00%.

Time to maximal drug concentration, t_{max}, will also be analyzed without transformation using a non-parametric method (Wilcoxon test). This analysis will only be performed for information purpose, not for BE assessment.

Additional details of statistical analysis methods will be included in the SAP.

12.3 Safety Evaluation

All safety data will be populated in the individual CRFs. All safety data will be listed by subjects.

Dosing dates and times will be listed by subject.

AEs will be coded using the most current version of Medical Dictionary for Regulatory Activities (MedDRA[®]) available at Celerion and summarized by treatment for the number of subjects reporting the TEAE and the number of TEAEs reported. A by-subject AE data listing including verbatim term, coded term, treatment, severity, and relationship to treatment will be provided.

Safety data including vital signs assessments and clinical laboratory evaluations will be summarized by treatment and point of time of collection.

Descriptive statistics using appropriate summary statistics will be calculated for quantitative safety data as well as for the difference to baseline, when appropriate. In addition, a shift table describing out of normal range shifts will be provided for clinical laboratory results.

Concomitant medications will be listed by subject and coded using the most current version of WHO drug dictionary available at Celerion. Medical history will be listed by subject.

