6 STUDY EVENTS FLOW CHART

Events and Assessments ^a	Screening ^b	Dose Period 1			Washout ^c	Dose Period 2			FU ^d
		Day -1 C-I	Day 1	Day 2		Day -1	Day 1	Day 2	
Informed Consent	X								
Demographic Information	X								
Complete Medical/Medication History	X								
Update to Medical/Medication History		X							
Full Physical Examination	X								
Brief Physical Examination ^e		X				X		X ⁿ	
Height, BMI	X								
Weight	X	X							
Vital Signs (Sitting HR, BP and T)	X		X ^g	X ^h			X ^g	X ^{h, n}	
Concomitant Medication Monitoring		X	X	X	X	X	X	X ⁿ	
Clinical Laboratory Evaluations, Fasted ⁱ (Hematology, Serum Chemistry, and Urinalysis)	X	X						X ⁿ	
Serum Pregnancy Test (♀ only)	X	X						X ⁿ	
Serum FSH (Postmenopausal ♀ only)	X								
Urine Drug / Alcohol / Cotinine Screen	X	X							
Serology (HIV, Hepatitis B, Hepatitis C)	X								
12-Lead Electrocardiogram	X		X ^f						
Study Drug Dosing ^j			X				X		
Begin Confinement		X ^k							
End Confinement								X ^l	
Blood for Pharmacokinetics			X ^m	X ^m			X ^m	X ^m	
Drug Dispensing and Accountability			X				X		
AE Monitoring			X	X	X	X	X	X ⁿ	X

- a: For details on Events and Assessments, refer to [Section 11](#).
- b: Within 21 days prior to the first study drug administration.
- c: There will be a washout period of at least 2 days between the 2 doses.
- d: The clinic will attempt to contact all subjects (including subjects who terminate the study early) using their standard procedures approximately 7 days after the last study drug administration to determine if any AEs has occurred since the last study visit.
- e: Symptom-driven physical examination may be performed at other times, at the PI or designee's discretion.
- f: Taken approximately 2 hours prior to dosing.
- g: Taken approximately 2 hours predose and at 2 hours postdose of each study drug.
- h: Taken after the 24-hour postdose PK blood sample is obtained.
- i: Subjects are reminded to fast for at least 8 hours prior to the blood draw for fasting clinical laboratory evaluation.
- j: Study drug will be administered after an overnight fast (for at least 10 hours), followed by another 4 hours of fasting postdose.
- k: Subjects will be admitted to the CRU on Day -1 of Dose Period 1, at the time indicated by the CRU.
- l: Subjects will be discharged from the CRU after the last PK sample and the vital signs measurements are obtained at 24 hours postdose in Dose Period 2.

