- m: Venous blood samples (10 mL each) will be collected at immediately (within 15 minutes) prior to dosing, and then at 0.5, 1, 1.5, 2, 2.5, 3, 3.5, 4, 4.5, 5, 5.5, 6, 6.5, 7, 7.5, 8, 9, 10, 11, 12, and 24 hours postdose.
- n: To be performed at the scheduled time or prior to early termination from the study.

Abbreviations: ♀ = Females, AE = Adverse event, BP = Blood pressure, C-I = Check-in, CRU = Clinical research unit, FSH = Follicle-stimulating hormone, FU = Follow-up, HIV = Human immunodeficiency virus, HR = Heart rate, PI = Principal Investigator, PK = Pharmacokinetic, T = Temperature.

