11.4 Blood Volume Drawn for Study Assessments

Table 1: Blood Volume during the Study

Sample Type	Number of Time Points	Approximate Volume per Time Point * (mL)	Approximate Sample Volume Over Course of Study (mL)
Screening laboratory safety tests (including hematology, serum chemistry, and serology), FSH (for postmenopausal female subjects only) and serum pregnancy (for female subjects only).	1	12.5	12.5
On-study hematology and serum chemistry (this includes serum pregnancy for female subjects only when scheduled at the same time)	2	12.5	25
Blood for MMF	44	10	440
Total Blood Volume (mL)→			477.5 **

* Represents the largest collection tube that may be used for this (a smaller tube may be used).

** If additional safety or PK analysis is necessary or if larger collection tubes are required to obtain sufficient plasma/serum for analysis, additional blood may be obtained (up to a maximum of 90 mL).

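### Laboratory results are to be summarised by treatment, but a completer's only scheduled post-dose panel comes after both products

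*Combined protocol and SAP*

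**What the plan says.** Section 12.3 puts two kinds of safety data under one rule: "Safety data including vital signs assessments and clinical laboratory evaluations will be summarized by treatment and point of time of collection". The next paragraph adds "Descriptive statistics using appropriate summary statistics will be calculated for quantitative safety data as well as for the difference to baseline, when appropriate" and then "In addition, a shift table describing out of normal range shifts will be provided for clinical laboratory results". The closing qualifier in the first of these applies to difference to baseline. Neither the by-treatment sentence nor the shift-table sentence carries a qualifier, and neither says how a result is assigned to a product.

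The timing comes from the flow chart in section 6, to which section 11.2.4 defers.

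- **Vital signs** have marks on Day 1 and Day 2 of both periods. The footnotes read "Taken approximately 2 hours predose and at 2 hours postdose of each study drug" and "Taken after the 24-hour postdose PK blood sample is obtained".
- **The laboratory row** ("Hematology, Serum Chemistry, and Urinalysis") has marks at Screening, Period 1 Day -1 and Period 2 Day 2. The last mark carries the footnote "To be performed at the scheduled time or prior to early termination from the study".

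Table 1 in section 11.4 gives 2 time points for "On-study hematology and serum chemistry (this includes serum pregnancy for female subjects only when scheduled at the same time"). Section 10.5.2 fixes the sequences as AB and BA. The Synopsis (Key Assessments) makes laboratory summary statistics optional and does not mention treatment. Section 12.2 leaves detailed methodology to a separate SAP, which is not in the text reviewed.

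**The concern.** A by-treatment table in a crossover is normally read as showing each product's own results in the same subjects. For laboratory tests the schedule cannot provide this. Nothing is measured between the two doses, so the first product has no post-dose result and the second has no baseline. Any change from baseline spans both doses.

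Safety and tolerability of each product is the secondary objective (section 9.1), and laboratory tests are a named safety endpoint (section 9.2). A table built literally from section 12.3 would place a value obtained after both products under the heading of one of them. A reader could take an out-of-range shift, or the absence of one, as evidence about that product alone.

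**Working it through.** **1. Count the scheduled panels.** The flow chart has nine columns: Screening; Period 1 Day -1, Day 1 and Day 2; Washout; Period 2 Day -1, Day 1 and Day 2; Follow-up.

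| Row | Columns marked |
|---|---|
| Laboratory panel | Screening; Period 1 Day -1; Period 2 Day 2 |
| Vital signs | Screening; Period 1 Days 1 and 2; Period 2 Days 1 and 2 |
| Dosing | Period 1 Day 1; Period 2 Day 1 |

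The laboratory row has two on-study marks, one before dose 1 and one after dose 2, and none between.

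**2. Check against Table 1.** Table 1 also gives 2 on-study time points: 2 × 12.5 = 25 mL. Its total reproduces: 12.5 + 25 + 44 × 10 = 477.5 mL. Two independent parts of the protocol agree, so the empty cells are not an artefact of how the flow chart was read.

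**3. Panels per exposure if all 50 dosed subjects (section 12.2.1) complete.**

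- Exposures: 50 × 2 = 100.
- Scheduled post-dose laboratory panels: 50 × 1 = 50, or 50/100 = 0.5 per exposure. All 50 follow both products.
- First-period exposures with their own panel: 0 of 50.
- Post-dose vital-sign readings: (2 h + 24 h) × 2 periods = 4 per subject, so 50 × 4 = 200, or 200/100 = 2 per exposure.

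**4. Baseline.** The two scheduled pre-dose panels (Screening and Period 1 Day -1) both precede dose 1. Whichever is used, a completer's change or shift to Period 2 Day 2 covers both doses. It also covers the pharmacokinetic sampling: 22 samples × 2 periods × 10 mL = 440 mL, which could itself move hematology values.

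**5. Early terminations.** Suppose *k* subjects leave between the doses and their early-termination panel is obtained. Exposures are then 100 − *k*; *k* panels follow one product and 50 − *k* follow both. The documents do not give *k*, so the values below are assumptions. The last equals the full allowance of 6 in section 12.2.1.

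| *k* | Panels after one product | Panels after both | First-period exposures with own panel |
|---|---|---|---|
| 0 | 0 | 50 | 0% |
| 1 | 1 | 49 | 1/50 = 2% |
| 3 | 3 | 47 | 3/50 = 6% |
| 5 | 5 | 45 | 5/50 = 10% |
| 6 | 6 | 44 | 6/50 = 12% |

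Unscheduled tests under section 11.2.4 are discretionary and cannot be counted in advance.

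**The case against.** The best defence is that the last panel can fairly be assigned to the last product received. Section 8.1.1 gives MMF a half-life of about 1 hour, with none circulating at 24 hours in most people, and section 8.2.1 regards the washout as long enough to prevent carryover. The Period 2 Day 2 panel comes about a day after dose 2 and at least 3 days after dose 1 (2 + 1). With both sequences used, each product would have a column. On this view section 12.3 only lacks an attribution rule, which the SAP could supply; section 12.2 allows it to modify the protocol's plans. Results, dosing dates and dosing times are all to be listed by subject, so what preceded each sample can be traced. Both products also deliver the same measured moiety.

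Part of this stands. A table by last product received can be produced, the SAP could define it, and the listings limit the harm.

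It does not rescue the sentence as written:

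- Section 12.3 states no such convention.
- Under that convention first-period exposures drop out, and the table compares the two sequence groups, with each completer under one product only.
- Clearance of the drug from plasma does not show that laboratory effects have ended, and change from baseline still spans both doses.
- The SAP can relabel a column but cannot create a between-dose result.

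**Conclusion.** The concern holds. Section 12.3 sets a by-treatment rule for laboratory data that the visit schedule does not support for completers. With full completion, all 50 scheduled post-dose panels follow both products and 0 of 50 first-period exposures has its own result. Even if all 6 subjects in the allowance left between doses and had their panel taken, the figure would be 6 of 50.

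The consequence is small. Only descriptive laboratory tables and the shift table are affected. The bioequivalence analysis, sample size, adverse event summaries and vital-sign summaries are untouched. By-subject listings, and investigator assessment of abnormal findings reported as adverse events, still capture individual signals. The instruction should nonetheless be corrected before it is carried into table shells.

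The conclusion rests on the flow chart and Table 1, which agree. It concerns scheduled panels; early-termination and discretionary tests are the exceptions.

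**What to change.** In section 12.3, limit the by-treatment sentence to vital signs, leave adverse events by treatment, and add text such as:

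> Clinical laboratory results, change from the Period 1 Day -1 baseline, and the shift table will be summarised overall by time point (baseline; end of study or early termination). In these summary tables, changes in subjects who received both products are not attributed to a single product.

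Keep early-termination panels in the summary and the shift table. Show in the by-subject laboratory listing which product or products preceded each sample. Investigator causality assessment of laboratory findings reported as adverse events (sections 11.2.5.1 and 11.2.5.3) does not change.

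If a split display is wanted, which would keep the sequence information that pooling loses, head its columns by sequence (AB, BA) or by last product received, with a note that a completer's panel follows both products.

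Reconcile the Synopsis, where laboratory summaries are optional, with section 12.3, where they are a commitment.

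The cost is a few lines in section 12.3 and the Synopsis, and matching SAP text. No sampling is added. The one loss is the by-treatment laboratory table, which the schedule does not support.

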13 STUDY ADMINISTRATION

13.1 Ethics

13.1.1 Institutional Review Board

This protocol will be reviewed by the Chesapeake Research Review, Inc. IRB, and the study will not start until the IRB has approved the protocol or a modification thereof. The IRB is constituted and operates in accordance with the principles and requirements described in the US Code of Federal Regulations (21 CFR Part 56). The IRB is compliant to International Conference on Harmonisation (ICH) guidelines, and may be reached at:

Chesapeake IRB
[name]
[name]
[contact]

13.1.2 Ethical Conduct of the Study

This research will be carried out in accordance with the protocol, US Code of Federal Regulations, 21 CFR Parts 50, 56, and 312, the ethical principles set forth in the Declaration of Helsinki, GCP, and the ICH harmonized tripartite guideline regarding GCP (E6 Consolidated Guidance, April 1996).

13.1.3 Subject Information and Consent

The purpose of the study, the procedures to be carried out and the potential hazards will be described to the subjects in non-technical terms. Subjects will be required to read, sign and date an ICF summarizing the discussion prior to screening, and will be assured that they may withdraw from the study at any time without jeopardizing their medical care.

Subjects will be given a copy of their signed ICF.

13.2 Termination of the Study

Celerion reserves the right to terminate the study in the interest of subject welfare.

13.3 Data Quality Assurance

Standard operating procedures are available for all activities performed at Celerion relevant to the quality of this study. Designated personnel of Celerion will be responsible for implementing and maintaining quality assurance (QA) and quality control systems to ensure that the study is conducted, and that data are generated, documented and reported in compliance with the study protocol, GCP and Good Laboratory Practice requirements as well as applicable regulatory requirements and local laws, rules and regulations relating to the conduct of the clinical study.

The Clinical Study Report will be audited by the QA department and the QA audit certificate will be included in the study report.

All clinical data will undergo a 100% quality control check prior to clinical database lock. Edit checks are then performed for appropriate databases as a validation routine using SAS[®] or comparable statistical program to check for missing data, data inconsistencies, data ranges, etc. Corrections are made prior to database lock.

13.4 Direct Access to Source Data/Documents

Celerion will ensure that the Sponsor, IRB and inspection by domestic and foreign regulatory authorities will have direct access to all study-related sites, source data/documents, and reports for the purpose of monitoring and auditing (ICH[E6] 5.1.2 & 6.10). In the event that other study-related monitoring should be done by other parties, they will be required to sign a confidentiality agreement prior to any monitoring and auditing.

13.5 Drug Supplies, Packaging and Labeling

The Sponsor will supply sufficient quantities of the study formulations to allow completion of this study. The lot numbers and expiration dates (where available) of the study drugs supplied will be recorded in the final report.

Records will be made of the receipt and dispensing of the study drugs supplied. At the conclusion of the study, any unused study drugs will be retained by Celerion, returned to the Sponsor or designee, or destroyed, as per Sponsor instructions. If no supplies remain, this fact will be documented in the pharmacy product accountability records.

13.6 Data Handling and Record Keeping

Celerion standard CRFs will be supplied. CRFs are printed off directly from the database. Each CRF is reviewed and signed by the PI.

All raw data generated in connection with this study, together with the original copy of the final report, will be retained by Celerion until at least 5 years after the last approval of a marketing application in an ICH region and until there are no pending or contemplated marketing applications in an ICH region or at least 5 years have elapsed since the formal discontinuation of clinical development of the investigational product. These documents should be retained for a longer period however if required by the applicable regulatory requirements or by an agreement with the sponsor. It is the responsibility of the Sponsor to inform the PI/Institution as to when these documents no longer need to be retained.

13.7 Report Format

Per the ICH Harmonized Tripartite Guideline (Organization of the Common Technical Document for the Registration of Pharmaceuticals for Human Use M4 and the ICH M2 Expert Working Group), a full final report will be written per the ICH E3 Guideline (Structure and Content of Clinical Study Reports).

13.8 Publication Policy

All unpublished information given to Celerion by the Sponsor shall not be published or disclosed to a third party without the prior written consent of the Sponsor.

The data generated by this study are considered confidential information and the property of the Sponsor. This confidential information may be published only in collaboration with participating personnel from the Sponsor or upon Sponsor's written consent to publish the article.

